6.1 Serious Adverse Event (SAE) Reporting

An adverse event or suspected adverse reaction is considered "serious" if, in the view of either the investigator or the sponsor, it results in any of the following outcomes:

- Death
- A life-threatening adverse drug experience – any adverse experience that places the patient, in the view of the initial reporter, at immediate risk of death from the adverse experience as it occurred. It does not include an adverse experience that, had it occurred in a more severe form, might have caused death.
- Inpatient hospitalization or prolongation of existing hospitalization
- A persistent or significant incapacity or substantial disruption of the ability to conduct normal life functions.
- A congenital anomaly/birth defect.

Important medical events that may not result in death, be life-threatening, or require hospitalization may be considered a serious adverse drug experience when, based upon appropriate medical judgment, they may jeopardize the patient or subject and may require medical or surgical intervention to prevent one of the outcomes listed in this definition.

Examples of such medical events include allergic bronchospasm requiring intensive treatment in an emergency room or at home, blood dyscrasias or convulsions that do not result in inpatient hospitalization, or the development of drug dependency or drug abuse (21 CFR 312.32).

- Important medical events as defined above, may also be considered serious adverse events. Any important medical event can and should be reported as an SAE if deemed appropriate by the Principal Investigator or the IND Sponsor, IND Office.
- All events occurring during the conduct of a protocol and meeting the definition of a SAE must be reported to the IRB in accordance with the timeframes and procedures outlined in "The University of Texas M. D. Anderson Cancer Center Institutional Review Board Policy for Investigators on Reporting Serious Unanticipated Adverse Events for Drugs and Devices". Unless stated otherwise in the protocol, all SAEs, expected or unexpected, must be reported to the IND Office, regardless of attribution (within 5 working days of knowledge of the event).
- All life-threatening or fatal events, that are unexpected, and related to the study drug, must have a written report submitted within 24 hours (next working day) of knowledge of the event to the Safety Project Manager in the IND Office. -
- OnCore, will be utilized for safety reporting to the IND Office and MDACC IRB.
- Serious adverse events will be captured from the time of the first protocol-specific intervention, until 30 days after the last dose of drug, unless the participant withdraws consent. Serious adverse events must be followed until clinical recovery is complete and laboratory tests have returned to baseline, progression of the event has stabilized, or there has been acceptable resolution of the event.
- Additionally, any serious adverse events that occur after the 30 day time period that are related to the study treatment must be reported to the IND Office. This may include the development of a secondary malignancy.

Reporting to FDA:

- Serious adverse events will be forwarded to FDA by the IND Sponsor (Safety Project Manager IND Office) according to 21 CFR 312.32. A copy of this form will be submitted to Stemline Therapeutics at the same time it is submitted to the IND Office.

It is the responsibility of the PI and the research team to ensure serious adverse events are reported according to the Code of Federal Regulations, Good Clinical Practices, the protocol guidelines, the sponsor's guidelines, and Institutional Review Board policy.

Recommended Adverse Event Recording Guidelines

Attribution	Grade 1	Grade 2	Grade 3	Grade 4	Grade 5
Unrelated	Phase I	Phase I	Phase I	Phase I	Phase I
			Phase II	Phase II	Phase II
				Phase III	Phase III
Unlikely	Phase I	Phase I	Phase I	Phase I	Phase I
			Phase II	Phase II	Phase II
				Phase III	Phase III
Possible	Phase I	Phase I	Phase I	Phase I	Phase I
	Phase II	Phase II	Phase II	Phase II	Phase II
		Phase III	Phase III	Phase III	Phase III
Probable	Phase I	Phase I	Phase I	Phase I	Phase I
	Phase II	Phase II	Phase II	Phase II	Phase II
		Phase III	Phase III	Phase III	Phase III
Definitive	Phase I	Phase I	Phase I	Phase I	Phase I
	Phase II	Phase II	Phase II	Phase II	Phase II
		Phase III	Phase III	Phase III	Phase III

7.0 Criteria for Removal from the Study

Participants will be removed from the study when any of the following criteria apply:

1. Patient withdrawal of the informed consent.
2. Patient's inability or unwillingness to have follow-up visits and/or laboratory tests required by this protocol.
3. General or specific circumstances, which render the participant unacceptable for further treatment in the judgment of the treating investigator.
4. An unexpected toxicity that is deemed unacceptable by the study chairman.
5. Disease progression.
6. After one year of treatment completion.
7. Death.
8. Lost to follow up

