5.2 Evaluations during follow up

All patients who do not discontinue study drug for toxicity will need to be followed for 30 days post-discontinuation to address any late developing toxicities which may occur. This follow up will cease when patients start a new therapy if prior to the 30-day follow up interval.

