5.3 Duration of follow up

Participants will be followed for one year after removal from protocol therapy with either clinic visit or a phone call, or until death, whichever occurs first. Participants removed from protocol therapy for unacceptable adverse event(s) will be followed until resolution or stabilization of the adverse event.

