Collection of adverse events will reflect the onset and resolution date and maximum grade. Intermittent events should be labeled as such and followed until resolution. If a patient is taken off study while an event still ongoing, this will be followed until resolution unless another therapy is initiated. Pre-existing medical conditions will be recorded only if an exacerbation occurs during the active treatment period.

Patients will be registered in MD Anderson's Clinical Trial Management System, OnCore.

Adverse events and all protocol specific data will be entered into the electronic case report form (REDCap).

Events not to be considered adverse events in this study are those related to original disease or expected in the post-allogeneic transplant period.

Isolated changes in laboratory parameters such as electrolyte, magnesium and metabolic imbalances, uric acid changes, elevations of LDH and alkaline phosphatase will not be monitored.

Concomitant medications

Patients treated on this protocol will require supportive care treatment (concomitant medications). These medications are considered standard of care and have no scientific contribution to the protocol; therefore no data will be captured on various medications needed or their side effects. All antiviral therapy will be captured in the medical record.

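### Sections 5.3 and 7.0 disagree on follow-up after disease progression, and Section 8.0 has no OS censoring rule for patients removed early; censoring at removal would bias Kaplan-Meier OS upward

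*Combined protocol and SAP*

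**What the plan says.** - **Section 7.0** opens with "Participants will be removed from the study when any of the following criteria apply". Its list includes "5. Disease progression". Item 6 is "After one year of treatment completion"; items 7 and 8 are death and loss to follow-up.
- **Section 5.3**: "Participants will be followed for one year after removal from protocol therapy with either clinic visit or a phone call, or until death", whichever comes first. It makes no exception for progression.
- **Section 4.7** lists progression among the events that stop treatment, so a progressed patient has left protocol therapy and comes within Section 5.3.
- **Section 3.1, inclusion criterion 13** requires that patients can comply with survival follow-up.
- **Section 8.0 (Analysis)** defines OS from treatment start to death, estimates it by Kaplan-Meier, and censors patients alive at study end. It does not define that date and has no rule for patients removed before it.
- **Section 1.0** makes estimation of OS one of two secondary objectives. **Section 2.3** names better OS as part of the rationale.

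**The concern.** One patient, at one event, gets two different instructions: a further year of contact (Section 5.3) or removal from the study now (Section 7.0). The choice decides whether deaths after relapse enter the OS analysis.

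Section 8.0 does not tell the analyst to censor at removal. But if Section 7.0 has been followed and no later vital status was collected, the removal date is the natural place to censor. That censoring would be informative: patients would leave the risk set at the moment their risk of death rises. Kaplan-Meier would then estimate survival as if relapse carried no extra mortality, in a study whose aim includes reducing relapse and improving survival.

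PFS is not affected by item 5, because progression is itself a PFS event.

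**Working it through.** The plan states no OS figure, event count or power, so there is no OS figure to reproduce. The check sizes the error if Section 7.0 governs and patients are censored at removal.

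**Inputs.** Section 2.2.4 gives 3-year rates from a 34-patient allo-HCT registry: relapse 32%, non-relapse mortality (NRM) 30%, DFS 33%, OS 41%. Relapse, NRM and DFS sum to 95% rather than 100%, so two fits are used, both matched to 3-year OS of 41%:
- Fit A keeps DFS at 33% (implying relapse 34.6%, NRM 32.4%).
- Fit B keeps relapse 32% and NRM 30% (implying DFS 38%).

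**Model.** Constant yearly hazards: hr for relapse, hn for death without relapse, mu for death after relapse.
- Total hazard before relapse: L = −ln(DFS)/3, split as hr = L × 32/62 and hn = L × 30/62.
- True OS(t) = exp(−Lt) + hr × [exp(−mu t) − exp(−Lt)] / (L − mu), with mu solved so that OS(3) = 0.41.
- Censoring at relapse: Kaplan-Meier converges to exp(−hn t).
- Following for one year after relapse (Section 5.3): the hazard seen is (hn A + mu B)/(A + B), where A is the proportion alive without relapse and B the proportion alive and relapsed within the last year.

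**Hazards.**
- Fit A: L = −ln(0.33)/3 = 0.3696; hr = 0.1907, hn = 0.1788, mu = 1.056 (median survival after relapse 7.9 months).
- Fit B: L = −ln(0.38)/3 = 0.3225; hr = 0.1665, hn = 0.1561, mu = 2.427 (median 3.4 months).

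In both, mu is well above hn (about 6 and 16 times), so the error is upward.

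| | True OS | Section 7.0, censored at removal | Section 5.3 |
|---|---|---|---|
| Fit A, 1 year | 78.6% | exp(−0.1788) = 83.6% (+5) | 78.6% (0) |
| Fit A, 2 years | 57.7% | exp(−0.3576) = 69.9% (+12) | 59.1% (+1.5) |
| Fit B, 1 year | 77.5% | exp(−0.1561) = 85.6% (+8) | 77.5% (0) |
| Fit B, 2 years | 56.6% | exp(−0.3121) = 73.2% (+17) | 57.2% (+0.6) |

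**Deaths not counted by 2 years, 20 patients.**
- Fit A: 20 × (1 − 0.5766) = 8.5 deaths, of which 20 × 0.2528 = 5.1 occur without relapse, leaving 3.4 after relapse.
- Fit B: 20 × (1 − 0.5655) = 8.7 deaths, 20 × 0.2300 = 4.6 without relapse, leaving 4.1.

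**Subgroups of the same registry, same 32/62 split, 2 years.**
- Transplanted in CR1 (DFS 36%, OS 52%): 71.9% against 66.5%, about +5.5.
- More advanced disease (DFS 26%, OS 29%): 64.8% against 45.4%, about +19.

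**Wider assumed range.** With 3-year relapse 20–50%, NRM 10–30% and median survival after relapse 3–24 months, the error from censoring at removal is +0.8 to +15.5 points at 1 year and +2.4 to +30.5 at 2 years. Under Section 5.3 it is 0 at 1 year and +0.3 to +2.3 at 2 years.

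**Against sampling noise.** In 10,000 simulated trials of 20 patients, the standard deviation of the 2-year estimate under censoring at removal was 11.5 points (A) and 10.8 (B). The errors are therefore about 1.1 and 1.5 standard deviations.

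No 3-year figure is claimed: a patient stopping after 24 cycles is followed for 24 × 28 + 365 = 1,037 days, short of three years.

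**The case against.** **The milder reading.** Item 5 may mean only that treatment ends. Items 3 ("General or specific circumstances, which render the participant unacceptable for further treatment in the judgment of the treating investigator") and 4 ("An unexpected toxicity that is deemed unacceptable by the study chairman") read as treatment reasons. Section 5.3 is the specific follow-up rule, has no progression exception, and continues to follow patients stopped for unacceptable adverse events. Section 6.0 says: "If a patient is taken off study while an event still ongoing, this will be followed until resolution unless another therapy is initiated". It also equates the end of active treatment with the last infusion, so item 6 could cover anyone who has stopped. This makes the milder reading plausible but does not settle it. Items 6, 7 and 8 end follow-up itself, and progression stands beside them as a separate criterion. The toxicity provisions do not secure vital status: those for ongoing events in Section 6.0 and for late toxicity in Section 5.2 ("This follow up will cease when patients start a new therapy if prior to the 30-day follow up interval") both lapse when other treatment begins. SAE capture closes 30 days after the last dose except for treatment-related events.

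**The bias is conditional.** Section 7.0 must prevail, later vital status must be absent, and the analyst must censor at removal. Read literally, censoring those alive at study end presupposes knowing their status then. That is right, and the finding is put conditionally.

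**The size may be overstated.** Fit B's 3.4-month median after relapse is near the short end of the assumed range, and the CR1 figures give a smaller error. If deaths within 30 days of relapse were still captured, with relapse at the last dose, the 2-year errors fall to about +10.5 (A) and +13 (B). A second US series in Section 2.2.4 (OS 68% at 1 year, 58% at 3 years) does not fit constant hazards. These points widen the uncertainty without changing the direction; the CR1 case lies within the stated range, and the advanced-disease case sits on the other side.

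**Conclusion.** The concern holds. The two sections are unreconciled for a progressed patient, and Section 8.0 lacks an OS censoring rule for anyone removed early. If Section 7.0 is followed and patients are censored at removal, 2-year Kaplan-Meier OS would be about 12 to 17 points too high on the registry fits, missing roughly 40% to 47% of expected deaths (3.4/8.5 and 4.1/8.7). If Section 5.3 is followed, the error is small.

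The direction needs only a higher death rate after relapse than before it. The size is illustrative: constant hazards, one small allo-HCT registry, auto-HCT patients also eligible, and an OS clock that starts between Day +45 and Day +180 after transplant.

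OS is descriptive and untested, and the tolerability endpoint, PFS, the 20-patient sample size and Tables 4 and 5 are unaffected. This should be fixed, but it does not threaten the primary result.

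**What to change.** Three sentences reconcile the text:

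1. **Section 7.0:** *Removal under items 3, 4 or 5 does not end the follow-up in Section 5.3.*
2. **Section 5.3:** state that vital status is also collected after disease progression, using the visit or telephone contact already provided there.
3. **Section 8.0:** *For OS, patients not known to have died are censored at the date last known alive.*

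The treatment-stopping rules in Section 4.7 are untouched. The cost is no contact beyond the year already planned, in at most 20 patients, and no change to sample size, stopping rule or primary endpoint. It should be done now, since vital status not collected during the study may not be recoverable at analysis. Follow-up beyond one year is optional and not part of this point.

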8.0 Statistical Considerations

Type of study: Open label, single-arm, single center, Phase 2 clinical trial

Number of patients planned: 20

Expected accrual rate: 5-10 patients/year

Toxicity monitoring

Continuous monitoring of toxicity will be performed in all 20 patients. The first 3 patients will be treated with 9 mcg/kg in first 4 cycles. From cycle 5 and beyond in the first 3 patients, the dose will be 12 ug/kg/day. All subsequent patients will be treated with 12 ug/kg/day. Unacceptable toxicities are defined as tagraxofusp-related toxicities which prevent initiation of Cycle 2 of therapy (Any adverse event ³ grade 3 that is both a) considered related to tagraxofusp, and b) does not resolve to \leq grade 2 after a maximum delay of 56-days). Assuming a prior beta distribution of (0.4, 1.6), corresponding to an unacceptable toxicity rate of 30%, treatment will terminate if the $Pr(dt > 0.20 | \text{data}) > 0.95$, where dt is the toxicity rate attributable to the tagraxofusp treatment. The decision rule for terminating for toxicity is presented in Table 4 and the software used for this Bayesian toxicity monitoring rule is Multc Lean version 2.1.0. The operating characteristics for this rule are presented in Table 5. The method used to produce the decision rule and operating characteristics was designed by Thall, Simon, and Estey ^{26, 27} and extended by Thall and Sung. ²⁸

Table 4 Stopping criteria

Total Patients Enrolled	Stopping Condition (# of patients experiencing unacceptable toxicities)
3-4	3-4
5-8	4-8
9-11	5-11
12-14	6-14
15-18	7-18
19	8-19
20	Patient enrollment ends

Table 5 Operating characteristics

True % of DLTs	Pr (stopping early)	Average # of patients treated
0.05	0.00	20
0.10	0.01	20
0.20	0.11	19
0.30	0.38	16
0.40	0.70	12
0.50	0.91	9

Analysis

Demographic and baseline characteristics will be summarized. Categorical measures will be summarized using frequencies and percentages while continuous variables will be summarized using mean, standard deviation, median, minimum, and maximum.

The primary endpoint of the study is the tolerability of tagraxofusp post-SCT, where tolerability is defined as receipt of at least 75% of planned tagraxofusp doses in at least 4 cycles of therapy. The following table shows the exact 95% confidence intervals for different percentages of patients, out of 20 patients, experiencing tolerability:

Patients experiencing tolerability		95% Exact
Number	Percentage	Confidence Interval
2	10%	1.2% - 31.7%
5	25%	8.7% - 49.1%
10	50%	27.2% - 72.8%
15	75%	50.9% - 91.3%

The percentage of patients considered 'tolerating' by this definition will be presented along with the associated 95% exact confidence interval.

PFS is defined as the duration from treatment start date to date of disease progression or death. Patients who are still alive at the end of the study with no evidence of disease will be censored. OS is defined as the time from treatment start date to death. Patients who are still alive at the end of the study will be censored. PFS and OS will be estimated using the Kaplan-Meier method. Median PFS and OS as well as rates with corresponding 95% confidence intervals will be presented.

Summary Reports

The Investigator is responsible for completing a toxicity/tolerability summary report, and submitting it to the IND Office Medical Affairs and Safety Group, for review and approval. This should be submitted after the first 3 evaluable patients, complete 1 cycle of study treatment, and every 2-3 evaluable patients, thereafter, following Table 4 stopping criteria guidelines.

For tolerability, an updated summary report should be submitted every 2-5 patients complete 4 cycles of study therapy, in accordance to the table located in the "Analysis" section of the protocol.

A copy of the toxicity summary should be placed in the Investigator's Regulatory Binder under "sponsor correspondence".

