2.3.2 Safety data

The most common individual treatment emergent adverse events (TEAEs) reported to date with tagraxofusp, regardless of dose, were ALT increased (69 patients, 55%) and AST increased (68 patients; 54%); hypoalbuminemia (66 patients; 53%); fatigue (61 patients, 49%); nausea (58 patients; 46%); peripheral edema (55 patients; 44%); pyrexia (54 patients; 43%); thrombocytopenia (44 patients; 35%), and headache and hyperglycemia (each 38 patients; 30%). A summary of the most common (i.e.; incidence ≥10%) TEAEs reported among tagraxofusp -treated patients, regardless of dose, is presented in Table 2. See Version 4.0 of the SL-401 Investigators Brochure for additional safety information.

Table 2. Most Common (≥ 10%) Treatment-Emergent Adverse Events, Overall and by Indication/Study, by MedDRA Preferred Term (Safety Population)

MedDRA Preferred Term	Stemline-Sponsored Study				Total	
	Study 0114 (BPDCN)	Study 0114 (AML)		Study 0314		
		(N=47) n (%)	(N=49) n (%)	(N=14) n (%)		
At least 1 TEAE	47 (100.0)	49 (100.0)	14 (100.0)	15 (100.0)	125 (100.0)	
Alanine aminotransferase increased	30 (63.8)		30 (61.2)	6 (42.9)	3 (20.0)69 (55.2)	
Aspartate aminotransferase increased	28 (59.6)		33 (67.3)	5 (35.7)	2 (13.3)68 (54.4)	
Hypoalbuminemia	26 (55.3)		30 (61.2)	7 (50.0)	3 (20.0)66 (52.8)	
Fatigue	21 (44.7)		27 (55.1)	6 (42.9)	7 (46.7)61 (48.8)	
Nausea	21 (44.7)		26 (53.1)	6 (42.9)	5 (33.3)58 (46.4)	
Oedema peripheral	24 (51.1)		19 (38.8)	3 (21.4)	9 (60.0)55 (44.0)	

		Stemline-Sponsored Study			
	Study 0114 (BPDCN)	Study 0114 (AML)	Study 0214	Study 0314	Total
Pyrexia	21 (44.7)		22 (44.9)	5 (35.7)	6 (40.0)54 (43.2)
Thrombocytopenia	23 (48.9)		11 (22.4)	6 (42.9)	4 (26.7)44 (35.2)
Headache	12 (25.5)		16 (32.7)	4 (28.6)	6 (40.0)38 (30.4)
Hyperglyc1emia	17 (36.2)		17 (34.7)	3 (21.4)	1 (6.7)38 (30.4)
Chills	16 (34.0)		12 (24.5)	5 (35.7)	3 (20.0)36 (28.8)
Dyspnea	6 (12.8)		18 (36.7)	3 (21.4)	9 (60.0)36 (28.8)
Anemia	11 (23.4)		13 (26.5)	3 (21.4)	7 (46.7)34 (27.2)
Hypotension	13 (27.7)		16 (32.7)	2 (14.3)	3 (20.0)34 (27.2)
Decreased appetite	12 (25.5)		15 (30.6)	2 (14.3)	4 (26.7)33 (26.4)
Weight increased	18 (38.3)		11 (22.4)	3 (21.4)	1 (6.7)33 (26.4)
Vomiting	8 (17.0)		14 (28.6)	3 (21.4)	5 (33.3)30 (24.0)
Diarrhea	7 (14.9)		13 (26.5)	3 (21.4)	6 (40.0)29 (23.2)
Dizziness	8 (17.0)		12 (24.5)	3 (21.4)	6 (40.0)29 (23.2)
Back pain	12 (25.5)		10 (20.4)	2 (14.3)	4 (26.7)28 (22.4)
Constipation	11 (23.4)		10 (20.4)	2 (14.3)	4 (26.7)27 (21.6)

		Stemline-Sponsored Study			

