4.4 Dose and schedule

First three patients:

- Cycles 1-4: Tagraxofusp 9 mcg/kg IV on Days 1, 2, and 3.
- Cycles 5 and beyond: Tagraxofusp 12 mcg/kg IV on Days 1 and 2 (if no unacceptable toxicities at the 9 ug/kg/day IV dose, as defined in the statistical section).

Patient number 4 and beyond:

- Cycles 1-4: Tagraxofusp 12 ug/kg/day IV on Days 1, 2, and 3.
- Cycles 5 and beyond: Tagraxofusp 12 ug/kg/day IV on Days 1 and 2.

Cycle Length: 28 days

During a 28-day cycle, if the patient experiences related non-hematological toxicity with resolution to Grade ≤ 1 or baseline by day 28, the tagraxofusp dose may be continued during the next cycle at the same dose.

Otherwise tagraxofusp-related non-hematological toxicity not resolved to Grade ≤ 1 or baseline by day 28, the start of the next cycle will be delayed until resolution to Grade ≤ 1 or baseline up to a maximum of additional 28 (56 total) days.

After this treatment delay dosing may be continued during the next cycle at same dose.

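### Does Table 5 misstate the toxicity stopping rule because patients 1-3 have their Cycle 1 at 9 mcg/kg and patients 4-20 at 12 mcg/kg?

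*Combined protocol and SAP*

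**What the plan says.** The toxicity monitoring text in section 8.0 covers all 20 patients with a single Bayesian rule. The event is defined there: "Unacceptable toxicities are defined as tagraxofusp-related toxicities which prevent initiation of Cycle 2 of therapy". It enters the rule through one parameter, "where dt is the toxicity rate attributable to the tagraxofusp treatment". Stopping is triggered when the posterior probability that this rate exceeds 0.20 is above 0.95, under a Beta(0.4, 1.6) prior. Table 4 gives the resulting counts for 3 to 19 patients, and Table 5 gives the operating characteristics, one true rate per row.

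The same paragraph sets out two dose levels: "The first 3 patients will be treated with 9 mcg/kg in first 4 cycles", and then "All subsequent patients will be treated with 12 ug/kg/day". Section 4.4 agrees. Patients 1-3 have "Cycles 1-4: Tagraxofusp 9 mcg/kg IV on Days 1, 2, and 3"; patients from number 4 on have "Cycles 1-4: Tagraxofusp 12 ug/kg/day IV on Days 1, 2, and 3". The move of the first three patients to 12 mcg/kg from cycle 5 is conditional: "if no unacceptable toxicities at the 9 ug/kg/day IV dose, as defined in the statistical section".

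The documents report no rate of the monitored event at either dose. The adverse event summary in section 2.3.2 covers events "reported to date with tagraxofusp, regardless of dose".

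**The concern.** An event that prevents Cycle 2 can only arise from Cycle 1. For patients 1-3 that means 9 mcg/kg; their later move to 12 mcg/kg falls outside the event window. For the other 17 it means 12 mcg/kg. The rule nevertheless adds the counts together, and Table 5 assigns all 20 patients one rate.

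If 9 mcg/kg were less toxic, three low-risk patients would sit at the front of the sequence and dilute the count. The rule would then stop less often, and later, than Table 5 suggests for a given rate at 12 mcg/kg. Safety is the primary objective and Table 5 is the plan's only statement of how often the rule stops. Someone who took its 40% row as a property of the 12 mcg/kg starting dose could believe the trial better protected than it is.

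**Working it through.** **Inputs.** From section 8.0: 20 patients, prior Beta(0.4, 1.6), threshold 0.20, cut-off 0.95, and the bounds b(n) of Table 4 (3 at n = 3-4, 4 at 5-8, 5 at 9-11, 6 at 12-14, 7 at 15-18, 8 at 19, none at 20). From sections 4.4 and 8.0: Cycle 1 at 9 mcg/kg for patients 1-3 and 12 mcg/kg for patients 4-20. Assumed, because the documents do not give them: the event rates p9 and p12 at the two doses.

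**Step 1: the bounds.** b(n) is the smallest x with Pr(Beta(0.4 + x, 1.6 + n - x) > 0.20) > 0.95. For example, at n = 5, x = 4 gives 0.993 and x = 3 gives 0.948; at n = 8, x = 4 gives 0.9504. Every Table 4 bound from n = 3 to 19 reproduces.

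**Step 2: Table 5 with one rate.** Let f(n, x) be the probability of still enrolling with x events after n patients. Then f(n, x) = f(n-1, x)(1 - p) + f(n-1, x-1)p. All mass with x ≥ b(n) is removed as stopped at n = 3, ..., 19.

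| True rate | Pr(stop), recomputed | Table 5 | Average N, recomputed | Table 5 |
|---|---|---|---|---|
| 0.05 | 0.001 | 0.00 | 20.0 | 20 |
| 0.10 | 0.009 | 0.01 | 19.9 | 20 |
| 0.20 | 0.108 | 0.11 | 18.8 | 19 |
| 0.30 | 0.376 | 0.38 | 16.0 | 16 |
| 0.40 | 0.701 | 0.70 | 12.2 | 12 |
| 0.50 | 0.910 | 0.91 | 8.7 | 9 |

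All six rows agree to rounding. Table 5 is thus a correct single-rate calculation with a check after each patient.

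**Step 3: two rates.** Same recursion and bounds, with p = p9 for patients 1-3 and p = p12 for patients 4-20. Cells show Pr(stop) / average N. The 75% column is what proportionality to dose would give, since 9/12 = 0.75.

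| p12 | p9 = p12 | p9 = 75% of p12 | p9 = 50% of p12 | p9 = 0 (extreme bound) |
|---|---|---|---|---|
| 0.20 | 0.11 / 18.8 | 0.08 / 19.1 | 0.06 / 19.4 | 0.03 / 19.8 |
| 0.30 | 0.38 / 16.0 | 0.32 / 16.9 | 0.26 / 17.7 | 0.16 / 18.9 |
| 0.40 | 0.70 / 12.2 | 0.64 / 13.5 | 0.57 / 14.8 | 0.43 / 17.0 |
| 0.50 | 0.91 / 8.7 | 0.87 / 10.2 | 0.83 / 11.6 | 0.72 / 14.3 |

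The direction depends on the assumption. With p9 = 0.40 and p12 = 0.30 the rule stops more often than printed: 0.46, with 14.7 treated.

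**Step 4: how much of the gap is pooling?** Only 17 patients start at 12 mcg/kg. The same bounds applied to those 17 alone (checks at 3 to 16) stop with probability 0.325 at a 30% rate and 0.625 at 40%. At p12 = 0.40 the pooled rule gives 0.636 when p9 = 0.30, 0.569 when p9 = 0.20 and 0.500 when p9 = 0.10. Pooling therefore costs nothing at p9 = 0.30 (0.625 - 0.636 = -0.011), about 6 points at 0.20 (0.625 - 0.569 = 0.056) and about 13 points at 0.10 (0.625 - 0.500 = 0.125). The break-even is p9 of about 28% at p12 = 0.40 and about 23% at p12 = 0.30.

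**Step 5: reading a row as the average rate over the 20 patients.** With p9 = 0.10 and p12 = 0.40 the average is (3 × 0.10 + 17 × 0.40)/20 = 0.355. A common rate of 0.355 gives 0.56, against 0.50 with two rates. With p9 = 0.20 the average is (3 × 0.20 + 17 × 0.40)/20 = 0.37, giving 0.61 against 0.57. On this reading Table 5 is off by about 4 to 6 points.

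**The case for a change.** The strongest case for a change is that the plan never says the two rates are taken as equal, and equality is as unproven as inequality. It makes the later dose of the first three patients conditional on their experience at 9 mcg/kg, so it treats the doses as distinct. Seventeen of 20 patients start at 12 mcg/kg, so a reader will naturally apply Table 5 to that dose. A 40% row that could be 0.57 or 0.64 instead of 0.70 deserves a note, which costs almost nothing.

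The factual part stands: the assumption is unstated and the two-rate arithmetic is right. The inference is weaker. Table 5 does not claim to describe 12 mcg/kg; its parameter refers to the treatment as given, and the two doses appear in the same paragraph. The condition in section 4.4 is a precaution before a dose change and says nothing about the expected size of any difference. The widest gaps need assumptions that nothing in the documents supports: p9 = 10% against p12 = 40% is a fourfold difference in rate for a 1.33-fold difference in dose.

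Two side points do not strengthen the case. Table 5 treats each outcome as known at once, although section 8.0 allows up to 56 days of delay before an event is established. That is a usual simplification, and the size of any effect depends on a lag model the plan does not contain. The Summary Reports text times reports at every two to three evaluable patients, whereas Table 5 assumes a check after each one. But section 8.0 calls for continuous monitoring and Table 4 has a bound at every count from 3 to 19. The reports document that check and do not replace it.

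**Conclusion.** The observation is correct, but it does not call for a change. Table 5 is right for the common rate it states, and no printed figure is in error. Whether a row also describes the 12 mcg/kg starting dose depends on a 9 mcg/kg rate the documents do not give. If that rate were 75% or 50% of the 12 mcg/kg rate, the probability of stopping would be 0.64 or 0.57 at 40% (printed 0.70) and 0.32 or 0.26 at 30% (printed 0.38). Much of that gap reflects having only 17 patients at that starting dose: on their own they give 0.63 and 0.33.

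Pooling three lead-in patients into the safety count of a 20-patient trial is a fair trade-off. It is neutral or better when the two rates are close and costs some sensitivity when they are far apart. A two-rate table would be a grid over assumed rates. It would move no boundary, dose, sample size, stopping decision or conclusion. A statistician reading Table 5 beside the dosing paragraph can see that its rows assume one rate, and can rerun the recursion with two if dose-specific rates become available.
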